# 3.2. BASELINE CHARACTERISTICS

# **BASELINE - DEMOGRAPHIC DATA**

Table 9: Baseline - Socio demographic data ITT

Age (years)		
N		
Mean (95%CI)		
SD		
Median (95%CI)		
Range		
Sex		
Female		
Male		
Race		
Caucasian		
Latin		

Table 10: Baseline - Socio demographic data PP

Age (years)		
N		
Mean (95%CI)		
SD		
Median (95%CI)		
Range		
Sex		
Female		
Male		
Race		

Table 11: Baseline - Physical characteristics ITT

Phototype (n(%))
Type I
Type II
Type III
Type IV
UK
Weight (kg)
N
Mean (95%CI)
SD
Median (95%CI)
Range
Height (cm)
Mean (95%CI)
SD
Median (95%CI)
Range Systolic Blood Pressure (mmHg)
N
Mean (95%CI)
SD
Median (95%CI)
Range Diastolic Blood Pressure (mmHg)
N
Mean (95%CI)
SD
Median (95%CI)
Range
Temperature (°C)
N
Mean (95%CI)
SD
Median (95%CI)
Range
Respiratory rate (BPM)
N
Mean (95%CI)
SD
Median (95%CI)
Range
Pulse Rate (BPM)
N
Mean (95%CI)
SD
Median (95%CI)
Range
rango

ECOG (n(%))
0
1
2
Barthel index (categorical), (n(%)),
previous to November 2020
Barthel index (Arbitrary units, scale 0-100)
N
Mean (95%CI)
SD
Median (95%CI)
Range
Barthel index modified, from November
2020
Barthel index modified (Arbitrary units,
scale 0-20), from November 2020
N CONTRACTOR OF THE PROPERTY O
Mean (SD)
Median
Range
Barthel index final (all values transformed
to scale 0-20) (categorical) (n(%))
Booth at the dess fine of feel fell control of some of
Barthel index final (all values transformed
to scale 0-20)
N Na (050/ O1)
Mean (95%CI)
SD Marking (050) (01)
Median (95%CI)
Range
Physical exam
Normal
Abnormal
Neurological exam
Normal
Abnormal
Ophthalmologic exam
Normal
Abnormal
Autoimmune concomitant diseases
Autoimmune concomitant diseases Yes
Autoimmune concomitant diseases

Table 12: Baseline - Physical characteristics PP

Phototype (n(%))		

Type I
Type II
Type III
Type IV
UK
Weight (kg)
N
Mean (95%CI)
SD
Median (95%CI)
Range
Height (cm)
N N
Mean (95%CI)
SD
Median (95%CI)
Range
Systolic Blood Pressure (mmHg)
N
Mean (95%CI)
SD
Median (95%CI)
Range
Diastolic Blood Pressure (mmHg)
N
Mean (95%CI)
SD
Median (95%CI)
Range
Temperature (°C)
N
Mean (95%CI)
SD
Median (95%CI)
Range
Respiratory rate (BPM)
N Market (05% O1)
Mean (95%CI)
SD No. 1000 (OD)
Median (95%CI)
Range
PulseRate (BPM)
N (OFFICE)
Mean (95%CI)
SD Marking (050(OI))
Median (95%CI)
Range
ECOG (n(%))
ECOG (n(%)) 0
ECOG (n(%)) 0 1
ECOG (n(%)) 0

Barthel index (categorical), (n(%)), previous to November 2020 Barthel index (Arbitrary units, scale 0-100) Mean (95%CI) SD Median (95%CI) Range Barthel index modified, from November 2020 Barthel index modified (Arbitrary units, scale 0-20), from November 2020 Ν Mean (SD) Median Range Barthel index final (all values transformed to scale 0-20) (categorical) (n(%)) Barthel index final (all values transformed to scale 0-20) Ν Mean (95%CI) SD Median (95%CI) Range Physical exam Normal Abnormal Neurological exam Normal Abnormal Ophthalmologic exam Normal Abnormal **Autoimmune concomitant diseases** Yes No UK

# 3.3. PREVIOUS MELANOMA HISTORY

Table 13: Previous Melanoma History ITT

Time since First diagnose date until	
treatment started (months)	
N	
Mean (95%CI)	

SD
Median (95%CI)
Range
Histological Subtype NA/UK
Superficial spreading
Nodular
Lentigo maligna
Others
Histological Subtype Others
Drimon, Molonomo I costion
Primary Melanoma Location NA/UK
Face
Scalp
Back
Upper extremities
Feet palms Chest
Abdomen
Others  Primary Malay and Lagation Others
Primary Melanoma Location Others
Duaviana Multiple Name
Previous Multiple Nevus
Yes No
NA/UK
Primary Melanoma Stage
In transit metastases
Yes
No
UK
Sentinel lymph node
Yes
No No
UK
Lymphadenectomy
Yes
No Luz
UK

Table 14: Previous Melanoma History PP

Time since First diagnose date until
treatment started (months)
N
Mean (95%CI)
SD

Median (95%CI)
Range
Histological Subtype
NA/UK
Superficial spreading
Nodular
Lentigo maligna
Others
Histological Subtype Others
Thistological dubtype others
Primary Melanoma Location
NA/UK
Face
Scalp
Back
Upper extremities
Feet palms
Chest
Abdomen
Others
Primary Melanoma Location Others
Timaly molaliona 2004 of Other
Previous Multiple Nevus
Yes
No
NA/UK
Primary Melanoma Stage
In transit metastases
Yes
No
UK
Sentinel lymph node
Yes
No
UK
Lymphadenectomy
Yes
No
UK

Figure 1: Heatmap BRAF ITT

Table 15: BRAF ITT

V600E
Missing data
Mutated
Not mutated
V600K
Mutated
Not mutated
NA/UK
V600E/K
Mutated
Not mutated
NA/UK
V600R
Mutated
Not mutated
NA/UK
V600 other
Mutated
Not mutated
NA/UK
V600 (NE)
Mutated
Not mutated
NA/UK

Table 16: BRAF PP

V600E	
Missing data	
Mutated	
Not mutated	
V600K	
Mutated	
Not mutated	
NA/UK	
V600E/K	
Mutated	
Not mutated	
NA/UK	
V600R	
Mutated	
Not mutated	
NA/UK	

V600 other	
Mutated	
Not mutated	
NA/UK	
V600 non specified	
Mutated	
Not mutated	
NA/UK	

Figure 2: Heatmap BRAF PP

Table 17: Other mutations ITT

RAS
Mutated
Not mutated
NA/UK
CKIT
Mutated
Not mutated
UK
GNAQ
Mutated
Not mutated
UK

Figure 3: Heatmap Other mutations ITT

Table 18: Other mutations PP

RAS		
Mutated		
Not mutated		
NA/UK		
CKIT		
Mutated		
Not mutated		
UK		
GNAQ		
Mutated		
Not mutated		
UK		

Figure 4: Heatmap Other mutations PP

Table 19: Adjuvant therapy ITT

Adjuvant therapy	
Yes	
No	
UK	
Previous adjuvant tx: Immunotherapy	
No	
Yes	
NA/UK	
Type of previous Immunotherapy	
Anti-PD1 + anti-CTLA4	
Anti-PD1 monotherapy	
Anti-PD1 monotherapy / Anti-PD1	
monotherapy	
NA/UK	
Previous adjuvant tx: Interferon	
No	
Yes	
NA/UK	
Previous adjuvant tx: Radiotherapy	
No	
Yes	
NA/UK	

Table 20: Adjuvant therapy PP

Adjuvant therapy	
Yes	
No	
UK	
Previous adjuvant tx: Immunotherapy	
No	
Yes	
NA/UK	
Type of previous Immunotherapy	
Anti-PD1 + anti-CTLA4	
Anti-PD1 monotherapy	
Anti-PD1 monotherapy / Anti-PD1	
monotherapy	
NA/UK	
Previous adjuvant tx: Interferon	
No	
Yes	
NA/UK	

Previous adjuvant tx: Radiotherapy	
No	
Yes	
NA/UK	

Table 21: Therapy for unresectable locally advanced or metastatic melanoma ITT

Therapy for unresectable locally advanced or
metastatic melanoma
Yes
No
Therapy for unresectable locally advanced or
metastatic melanoma: Mts Surgery
No
Yes
NA/UK
Therapy for unresectable locally advanced or
metastatic melanoma: Immunotherapy
No
Yes
NA/UK
Therapy for unresectable locally advanced or
metastatic melanoma: Type of Immunotherapy
Nivolumab
Nivolumab+ipilimumab
Pembrolizumab
NA/UK
Therapy for unresectable locally advanced or
metastatic melanoma: Radiotherapy
No
Yes
NA/UK
Therapy for unresectable locally advanced or
metastatic melanoma: Segmentectomy
No
Yes
NA/UK
Therapy for unresectable locally advanced or
metastatic melanoma: Radiosurgery
No
Yes
NA/UK

Table 22: Therapy for unresectable locally advanced or metastatic melanoma PP

Therapy for unresectable locally advanced or
metastatic melanoma

V
Yes No
Therapy for unresectable locally advanced or
metastatic melanoma: Mts Surgery
No Yea
Yes
NA/UK
Therapy for unresectable locally advanced or
metastatic melanoma: Immunotherapy
No
Yes
NA/UK
Therapy for unresectable locally advanced or
metastatic melanoma: Type of Immunotherapy
Nivolumab
Nivolumab+ipilimumab
Pembrolizumab
NA/UK
Therapy for unresectable locally advanced or
metastatic melanoma: Radiotherapy
No
Yes
NA/UK
Therapy for unresectable locally advanced or
metastatic melanoma: Segmentectomy
No
Yes
NA/UK
Therapy for unresectable locally advanced or
metastatic melanoma: Radiosurgery
No
Yes
NA/UK

# 3.4. BASELINE CURRENT MELANOMA

# Table 23: Baseline Current Melanoma ITT

Time since diagnosis of current melanoma until treatment started (months)
N
Mean (95%CI)
SD
Median (95%CI)
Range
Current Melanoma Histological Subtype
Superficial spreading
Nodular
Lentigo maligna
UK

Others
listological subtype specify
Current Melanoma Stage
IV

Table 24: Baseline Current Melanoma PP

Time since diagnosis of current melanoma until
treatment started (months)
N .
Mean (95%CI)
SD
Median (95%CI)
Range
Current Melanoma Histological Subtype
Superficial spreading
Nodular
Lentigo maligna
UK
Others
Histological subtype specify
Current Melanoma Stage
IV

Table 25: TNM Current Melanoma ITT

Initial T Stage
T0
T1a
T1b
T2a
T2b
T3a
T3b
T4a
T4b
Tx
Initial N Stage
NO
N1a
N1b
N1c
N2a
N2b

N2c     N3b     N3c     Nx     Initial M Stage     M1d(0)     M1d(1)     Breslow (mm)     N     Mean (95%CI)     SD     Range     Mitotic Rate (mm^2)     N     Mean (95%CI)     SD     Range     Mitotic Rate (mm^2)     N     Mean (95%CI)     SD     Range     Uiceration     Yes		
N3b         N3c         Nx         Initial M Stage         M1d(0)         M1d(1)         Breslow (mm)         N         Mean (95%CI)         SD         Range         Mitotic Rate (mm^2)         N         Mean (95%CI)         SD         Range         Ulceration         Yes		
N3c         Nx         Initial M Stage         M1d(0)         M1d(1)         Breslow (mm)         N         Mean (95%CI)         SD         Range         Mitotic Rate (mm^2)         N         Mean (95%CI)         SD         Range         Ulceration         Yes	N2c	
Nx   Initial M Stage   M1d(0)   M1d(1)   Breslow (mm)   Man (95%CI)   SD   Range   Mitotic Rate (mm^2)   N   Mean (95%CI)   SD   Range   Man (95%CI)   SD   Range   Man (95%CI)   SD   Company   Man (95%CI)   Company   Man (95%CI)   Company   Man (95%CI)   Company   Man (95%CI)   Man (95%CI)	N3b	
M1d(0)	N3c	
M1d(0)	Nx	
M1d(1)  Breslow (mm)  N  Mean (95%CI)  SD  Range  Mitotic Rate (mm^2)  N  Mean (95%CI)  SD  Range  Ulceration		
M1d(1)         Breslow (mm)         N       Mean (95%CI)         SD       Range         Mitotic Rate (mm^2)         N       Mean (95%CI)         SD       Range         Ulceration         Yes		
N		
Mean (95%CI) SD Range Mitotic Rate (mm^2) N Mean (95%CI) SD Range Ulceration Yes		
SD Range Mitotic Rate (mm^2)  N Mean (95%CI) SD Range Ulceration Yes	N	
Range Mitotic Rate (mm^2)  N Mean (95%CI) SD Range Ulceration Yes	Mean (95%CI)	
Mitotic Rate (mm^2)  N Mean (95%CI) SD Range Ulceration Yes	SD	
Mitotic Rate (mm^2)  N Mean (95%CI) SD Range Ulceration Yes	Range	
N Mean (95%CI) SD Range Ulceration Yes		
SD Range Ulceration Yes		
Range Ulceration Yes	Mean (95%CI)	
Ves Ves	SD	
Yes	Range	
N.I.	Yes	
No	No	
LIK	UK	

Table 26: TNM Current Melanoma PP

Initial T Stage	
T0	
T1a	
T1b	
T2a	
T2b	
T3a	
T3b	
T4a	
T4b	
Tx	
Initial N Stage	
N0	
N1a	
N1b	
N1c	
N2a	
N2b	
N2c	
N3b	
N3c	
Nx Nx	
Initial M Stage	
M1d(0)	
M1d(1)	

Breslow (mm)
N
Mean (95%CI)
SD
Range
Mitotic Rate (mm^2)
N
Mean (95%CI)
SD
Range
Ulceration
Yes
No
UK

Table 27: Metastases ITT

Brain Metastases	
Unique	
Multiple	
Target Brain Metastases	
1	
2	
3	
4	
5	
UK	
Extracranial Metastases	
Yes	
No	
Lung Metastases	
Yes	
No	
UK	
Lung Metastases Number	
1	
_ 2	
3	
4	
>5	
NA/UK	
Liver Metastases	
Yes	
No	
UK	
Liver Metastases Number	
1	
2	
3	

>5
NA/UK
Skin Metastases
Yes
No
UK
Skin Metastases Number
1
2
3
>5
UK
Bone Metastases
Yes
No
UK
Bone Metastases Number
1
2
NA/UK
Pleura Metastases
Yes
No
UK
Pleural Effusion Volume
0
NA/UK
Soft Tissue Metastases
Yes
No
UK
Soft Tissue Metastases Number
1
5
NA/UK
Lymph Nodes Metastases
Yes
No
UK
Lymph Nodes Metastases Number
1
2
3
>5
UK
NA/UK
Peritoneum Metastases
Yes No
UK
Peritoneum Metastases Number

1
NA/UK
Other Metastases
Yes
No
UK
Other Metastases Number
1
2
>5
UK
Other Metastases Specify

# Table 28: Metastases PP

Brain Metastases
Unique
Multiple
Target Brain Metastases
1
2
3
4
5
UK
Extracranial Metastases
Yes
No
Lung Metastases
Yes
No
UK
Lung Metastases Number
1
2
3
4
>5
NA/UK
Liver Metastases
Yes
No
UK
Liver Metastases Number
1
2
3
>5
NA/UK
Skin Metastases

Yes
No
UK
Skin Metastases Number
1
2
3
>5
UK
Bone Metastases
Yes
No
UK
Bone Metastases Number
1
2
NA/UK
Pleura Metastases
Yes
No
UK
Pleural Effusion Volume
0
NA/UK
Soft Tissue Metastases
Yes
No
UK
Soft Tissue Metastases Number
1
5
NA/UK
Lymph Nodes Metastases
Yes
No
UK
Lymph Nodes Metastases Number
1
2
3
>5
NA/UK
Peritoneum Metastases
Yes
No
UK
Peritoneum Metastases Number
1
NA/UK
Other Metastases
Yes

No
UK
Other Metastases Number
1
2
>5
UK
Other Metastases Specify
· · ·

Table 29: LDH concentration and corticosteriods ITT

LDH Concentration
Normal (≤ULN)
Elevated (>ULN)
UK
Corticosteroids Treatment
Yes
No
Corticosteroids Treatment Type
Missing data
Dexamethasone
Metilprednisolona
Prednisone
UK
Administration
Stable
Decreasing
NA

Table 30: LDH concentration and corticosteriods PP

LDH Concentration
Normal (≤ULN)
Elevated (>ULN)
UK
Corticosteroids Treatment
Yes
No
Corticosteroids Treatment Type
Missing data
Dexamethasone
Metilprednisolona
Prednisone
UK
Administration
Stable

Decreasing			
NA			

# 3.4.1.BASELINE TUMOR BURDEN

Table 31: Brain Tumor burden (mm) ITT

Brain Tumor burden (mm) intracranial				
Target lessions				
N				
Mean (95%CI)				
SD				
Median (95%CI)				
Range				

Table 32: Brain Tumor burden (mm) PP

Brain Tumor burden (mm) intracranial				
Target lessions				
N				
Mean (95%CI)				
SD				
Median (95%CI)				
Range				

# 3.5. TREATMENT COMPLIANCE

Upon database closure, there are 4 patients still undergoing treatment.

### 3.5.1. BINIMETINIB COMPLIANCE

Table 33: Incidence reason for Binimetinib

Incidence	
N	
No	
Yes	
Delay	
Not available	
N	
No	
Yes	
Reduction	

Not available			
N			
No			
Yes			
End of treatmer	nt¹		
Not available			
N			
No			
Yes			
Interruption due to local treatment			
Not available			
N			
No			
Yes			
Interruption due to s	urgery		
Not available			
N			
No			
Yes			

 The End of Treatment variable only reports 'Yes' incidents that were caused by 'End of Treatment'

Table 34: Reasons for incidence (free field to review)

PatientNumb	IncidenceSta	IncidenceEn	Incidence	Reason	End of treatment
er.Inc	rtDate	dDate	Incluence	Neason	reason compiled

Table 35: Binimetinib Treatment duration (months)

Binimetinib gross duration time (months)				
Missing				
N				
Mean (95%CI)				
SD				
Median (95%CI)				
Range				
Binimetinib net duration time (months)				
Missing				
N				
Mean (95%CI)				

SD	
Median (95%CI)	
Range	

# 3.5.2. ENCORAFENIB COMPLIANCE

Table 36: Incidence reason for Encorafenib

Incidence
N
No
Yes
Delay
Not available
N
No
Yes
Reduction
Not available
N
No
Yes
End of treatment 
Not available
N
No
Yes
Interruption due to local treatment
Not available
N
No
Yes
Interruption due to surgery
Not available
N
No
Yes
(1) The End of Treatment variable only reports 'Var

 The End of Treatment variable only reports 'Yes' incidents that were caused by 'End of Treatment'

Table 37: Encorafenib Treatment duration (months)

# Encorafenib gross duration time (months) Missing N Mean (95%CI) SD Median (95%CI) Range Encorafenib net duration time (months) Missing N Mean (95%CI) SD Median (95%CI) SD Median (95%CI) Range

Table 38: Reasons for incidence (free field to review)

PatientNumb IncidenceSta I	ncidenceEn	Incidence	Reason	End of treatment
er.Inc rtDate	dDate	incidence	Reason	reason compiled

# 4. PRIMARY EFFICACY OBJECTIVE

# 4.1. ITT PRIMARY EFFICACY OBJECTIVE: RESPONSE AT 56 DAYS

Table 39: Primary Efficacy Objective. Day 56 Evaluation. ITT

intracranial Evaluation at 56 days	
CR	
PR	
SD	
PD	
NE	

Table 40: ITT: intracranial Objective Response Rate at 56 days

All patients: ORR intracranial response	
CR or PR	

All patients: ORR intracranial response	
SD or PD	
NE	
Total	
Cohort 1: ORR intracranial response	
CR or PR	
SD or PD	
NE	
Total	
Cohort 2: ORR intracranial response	
CR or PR	
SD or PD	
Total	

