## 4.2. Study Objectives

## 1. Primary objective:

a. Intracranial objective response rate by modified RECIST 1.1 before local treatment in cohort 1 and in cohort 2.

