## 5.3. Patient Inclusion and Cohort Assignment

During the screening (28 days before day 1 cycle 1) it should be assessed whether the patient is symptomatic (cohort 2) or asymptomatic (cohort 1).

Definition of Asymptomatic (cohort 1):.Patients without active symptoms secondary to brain metastases at the moment of inclusion.

After confirming that a patient fulfils all eligibility criteria of the study (inclusion/exclusion criteria), site staff will initiate the eCRF registration procedure.

Once procedure is fulfilled the site staff will receive the "Inclusion confirmation communication", and protocol-specific treatment can be initiated.

This is an open label, single arm study including two cohorts of patients, in each cohort, patients will be treated with encorafenib 450 mg once daily and binimetinib 45 mg twice daily.

After 56 days of treatment, a contrast enhanced brain MRI and CT body scan will be performed as first tumour assessment:

- Patients with PD at first evaluation in brain MRI (modified RECIST 1.1 criteria) and /or body CT scan (RECIST 1.1 criteria) will discontinue study treatment and will continue in the study for OS follow-up.
- Patients with CR in brain (modified RECIST 1.1) and no PD in the body (RECIST 1.1), will continue study treatment and will be followed every two months with contrast enhanced brain MRI and body CT scan up to 12 months. If no PD after one year, patients will be followed as per institutional criteria, and continue with the treatment.
  - o If considered by the investigator, local treatment can be done for brain CR patients, but only after confirming no safety concerns (defined as substantial deterioration of vital signs (including ECOG PS), physical examination, ECG, Lab. Values that do not recommend RT) with the three first patients treated with radiation therapy in the running phase (for more information, please see section 9.1).
- Patients with no CR and no PD in brain MRI per modified RECIST 1.1 criteria, and no PD in body per RECIST 1.1 criteria, will be treated with local RT and/or radiosurgery, and then will continue Enco and Bini. The first 3 patients will be treated in a running

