phase. These three first patients, that have achieved non-CR, non-PD in brain and no PD in body, are going to be treated sequentially or at the same time depending on when radiotherapy treatment is needed. If no safety concerns appear (defined as substantial deterioration of vital signs (including ECOG PS), physical examination, ECG, Lab. Values that do not recommend RT), the rest of patients that have achieved non-CR, non-PD in brain will begin local treatment when it will be indicated under medical criteria:

- Encorafenib and binimetinib will be interrupted 24h before radiotherapy and restart 24h after the last dose of radiotherapy.
- The local radiation technique will be defined and indicated by the radiotherapy oncologist (local co-investigator) criteria, depending on the number of lesions and its maximum size in the last tumour assessment done during the treatment with encorafenib and binimetinib:
  - \*Radiosurgery (RS) or Stereotactic radiosurgery (SRS):
    - 1 brain metastases < 4 cm
    - ≤ 3 brain metastases ≤ 3 cm
    - ≤ 4 brain metastases ≤ 2.5 cm

\*Radiosurgery: for patients who do not meet criteria for radiosurgery (RS) or (SRS), exceptional cases could be allowed after prior detailed consultation with the trial coordinators.

- Whole brain radiotherapy (WBRT):
  - ≥ 4 brain metastases
  - Almost one brain metastasis of ≥ 4 cm
  - ≤ 4 brain metastases not eligible for RS or SRS

Location metastases: brain stem, midbrain, pons, medulla or within 10 mm of the optic nerves and chiasm.

- After the first evaluation of the patient's intracranial response, patients without progression who received a local treatment, could receive other local treatments at the discretion of the investigator, if this is considered beneficial for the patient.
- Surgery can be done if, as per investigator criteria, is necessary for the patient's health.
- For patients in CR in the first assessment, if they were not treated with radiation, and in follow up a PD occurs **only in the brain**, brain local treatment will be carried out as per protocol. These patients can continue encorafenib and binimetinib treatment after local treatment.
- Every patient with a stable disease or response in both, brain and body, in the first assessment, when presenting a DP after local treatment in the body CT scan by RECIST 1.1. and/or brain MRI, by modified RECIST 1.1, they will discontinue the systemic treatment with encorafenib and binimetinib.

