# 10.2. Study endpoints

Intracranial objective response (iORR) rate by modified RECIST 1.1 before local treatment in cohort 1 and 2: iORR calculated as the proportion of patient with a best overall intracranial response of complete response (CR) or partial response (PR) before local treatment in cohort 1 and 2. The final statistical analysis of this endpoint is expected to be performed within 3 months after the local treatment of the last patient in any cohort. iORR will be also reported separately for both cohorts.

**Duration of intracranial response in both cohorts (iDOR):** Calculated as the time from the date of first documented CR or PR to the first documented intracranial progression or death due to underlying cancer, in patients with documented intracranial CR or PR before local treatment. The final statistical analysis of this endpoint is expected to be performed within 6 months after database closure expected at 24 months after last patient inclusion, however interim analysis might be performed when analysing other primary variables.

The intracranial progression free survival (iPFS) by modified RECIST in both cohorts: iPFS is defined as the time from the date of inclusion to the date of the first documented intracranial disease progression or death due to any cause, whichever occurs first. PFS will be determined based on tumour assessment (modified RECIST version 1.1 criteria). The local Investigator's assessments will be used for analyses. Those patients who are alive and have not progressed at the last follow-up, date of progression will be censored at the date of the last follow-up. Patient with no additional image test other than baseline will be censored to the day after to inclusion. The final statistical analysis of this endpoint is expected to be performed within 6 months after database closure expected at 24 months after last patient inclusion, however interim analysis might be performed when analysing other primary variables.

Percentage of patients free of intracranial progression at 6 (week 24), 12 (week 48) and 24 months (week 96) in both cohorts: percentage of patients free of intracranial progression assessed by modified RECIST at 6 months (week 24), 12 months (week 48) and 24-month (week 96) considering date of inclusion. The final statistical analysis of this endpoint is expected to be

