# 4.2. PP PRIMARY EFFICACY OBJECTIVE: RESPONSE AT 56 DAYS

Table 41: Primary Efficacy Objective. Day 56 Evaluation. PP

intracranial Evaluation at 56 days	
CR	
PR	
SD	
PD	
NE	

Table 42: PP: intracranial Objective Response Rate at 56 days

All patients: ORR intracranial response	
CR or PR	
SD or PD	

All patients: ORR intracranial response
NE
Total
Cohort 1: ORR intracranial response
CR or PR
SD or PD
NE
Total
Cohort 2: ORR intracranial response
CR or PR
SD or PD
NE
Total

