# 4.3. RADIOTHERAPY TREATMENT

### **ITT: RADIOTHERAPY TREATMENT**

Table 45: Radiotherapy treatment. ITT

Radiotherapy treatment (Local and/or Whole Brain)  N  Yes	
Yes	
Yes (CR) 	
No	
No (CR)	
LocaL Radiation treatment	
N	
Yes	
Yes (CR)	
No	
No (CR)	
Local Radiation Treatment type	
N	
No	
Radiosurgery (RS)	

Stereotactic radiosurgery (SRS)	
Device Used	
Missing	
N	
Gamma Knife	
Accelerator Linac-Based Systems (IMRT, Rapid Arc, VMAT)	
Cyberknife	
Whole Brain Radiotherapy	
N	
Yes	
No	
No (CR)	

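### The protocol's primary endpoint is best intracranial response before local treatment, but the SAP computes only the day-56 response, which can equal or understate it

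*Combined protocol and SAP*

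**What the plan says.** **Protocol.** The primary objective (section 4.2) is "Intracranial objective response rate by modified RECIST 1.1 before local treatment in cohort 1 and in cohort 2". It names no day. Section 10.2 makes it operational: "iORR calculated as the proportion of patient with a best overall intracranial response of complete response (CR) or partial response (PR) before local treatment". This is a best response over a window that closes at local treatment.

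**SAP.** Section 4.1 is headed "ITT PRIMARY EFFICACY OBJECTIVE: RESPONSE AT 56 DAYS". Section 4.2 does the same for the per-protocol set, with Table 42 titled "PP: intracranial Objective Response Rate at 56 days". Section 7.3 repeats the day-56 response for the symptomatic and asymptomatic regroupings. No SAP table gives best response before local treatment, and no SAP sentence says that the two are the same.

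**Timing.** Protocol 5.3 fixes the first scan: "After 56 days of treatment, a contrast enhanced brain MRI and CT body scan will be performed as first tumour assessment". Patients with neither CR nor PD in the brain, and no systemic PD, then go to local radiotherapy. Once the first three irradiated patients raise no safety concern, the remainder "will begin local treatment when it will be indicated under medical criteria"; no deadline is given. Section 8.1 schedules brain MRI every 8 weeks up to 12 months and lets the investigator order further scans at any time.

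**The concern.** A best response over a window and a response at one visit are different variables. They give the same count only when no scan other than day 56 can change a patient's classification before local treatment. The protocol makes that the usual case but does not guarantee it: radiotherapy may start later than the next scan, and unscheduled scans are allowed.

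A programmer following the SAP would then count some protocol-defined responders as non-responders on the primary endpoint. Duration of response is affected too. Protocol 10.2 restricts it to patients who responded before local treatment, while SAP Tables 43 and 44 do not say which responders they include. A reader comparing the report with the protocol could not tell whether the published rate is the protocol's endpoint.

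**Working it through.** **1. The plan's own sample size (protocol 10.1).** Inputs: null rate 40%, alternative 60%, one-sided 5%, power 80%, 20% not evaluable.

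n = [(z₀.₉₅·√(p₀(1−p₀)) + z₀.₈₀·√(p₁(1−p₁))) / (p₁−p₀)]²
= [(1.645·√0.24 + 0.842·√0.24) / 0.20]² = 37.1, rounded up to 38.

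38 / (1 − 0.20) = 47.5, rounded up to 48. Both planned figures reproduce. Aligning the endpoint definition does not change them.

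**2. Where the definitions agree and differ.**

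| Day-56 brain result | Other brain MRI before local treatment | Protocol 10.2 | SAP 4.1–4.2 |
|---|---|---|---|
| CR or PR | any | responder | responder |
| SD or NE | CR or PR on a later scan | responder | not a responder |
| PD or NE | CR or PR on an unscheduled scan before day 56 | responder | not a responder |
| SD, PD or NE | no CR or PR | not a responder | not a responder |

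The table assumes that local treatment has not been given before the day-56 scan. A day-56 CR or PR counts under both definitions, so only patients who are not responders at day 56 can be discordant. Every day-56 responder is also a protocol responder, so the SAP numerator is at most the protocol numerator.

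The exception is local treatment before the day-56 scan. Protocol 5.3 allows surgery when the investigator judges it necessary and sets no time limit. The protocol's window would then have closed before day 56. Section 10.3 makes intracranial lesions non-evaluable after local treatment, which limits this route but does not settle how the SAP tables would code such a patient.

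**3. Size per discordant patient.** The shift is k/N, where k is the number of discordant patients. The documents do not give k, so the range below is an assumption.

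| k (assumed) | N=63 (48+15) | N=48 (cohort 1) |
|---|---|---|
| 1 | 1.6 points | 2.1 points |
| 2 | 3.2 | 4.2 |
| 5 | 7.9 | 10.4 |

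**4. What one patient could change (illustration).** Exact one-sided binomial tail probabilities against 40%:

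- N=63: 32 responders give p=0.054, and 33 give p=0.031.
- N=48: 25 responders give p=0.060, and 26 give p=0.033.

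Under the success rule of protocol 4.1, a rate of at least 40%, the step at N=63 falls between 25 responders (25/63 = 39.7%) and 26 (26/63 = 41.3%). One patient matters only if the observed count lies at such a step.

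**The case against.** The best defence is that the SAP simply puts the protocol's endpoint into practice. Day 56 is the first scheduled scan, PD at that scan ends study treatment, CR counts either way, and the others go to radiotherapy. Protocol 10.1 treats patients without the first assessment around day 56 as the non-evaluable ones, and the SAP's per-protocol set requires baseline plus the first assessment. Discordance needs either radiotherapy deferred by about 8 weeks, to the next scheduled MRI, or an off-schedule scan. The documents do not say how often either happens. This stands as a reason to expect few discordant patients. It does not make the definitions identical, and nothing in the SAP says that they are.

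A reader might go further in three ways that the documents do not support.

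- **That the definitions agree only if every SD or PR patient is irradiated at once.** A day-56 PR is a responder under both, whenever radiotherapy follows.
- **That "Table 45: Radiotherapy treatment. ITT" shows SD or PR patients left without radiotherapy, because its No row is separate from its No (CR) row.** Patients with PD at day 56, and those who die or are lost before it, also belong in the No row. It would be needed even if every SD patient were irradiated promptly.
- **That the SAP picked the more favourable count.** SAP 3.5 reports the number of patients still on treatment at database closure, so some of its text was written with data in hand. But the only count it tabulates is the stricter one, apart from the local-treatment exception above, and the documents do not show when or why day 56 was chosen.

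**Conclusion.** The mismatch is real and concerns the primary endpoint: the protocol specifies best response before local treatment, and the SAP computes response at day 56 only. For most patients the two agree by design. Where they differ, the day-56 numerator falls short of the protocol numerator, provided local treatment does not precede the day-56 scan.

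The size cannot be obtained from the documents. It is 1.6 points (N=63) or 2.1 points (N=48) per discordant patient, and probably small in total. The p-values above should not be read as the trial's decision rule: the one-sided 5% design was set for cohort 1, and neither document states an exact test on the pooled 63 patients. The point is that the SAP should compute what the protocol defines; it is not evidence that the result is inflated.

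**What to change.** In SAP 4.1 and 4.2:

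- Derive the primary iORR as protocol 10.2 defines it: best response on all brain MRIs before the first day of local treatment, with all included patients in the ITT denominator.
- State where the window closes for patients who never receive local treatment, since protocol 10.2 does not say, and how a day-56 NE or surgery before day 56 is handled.
- Use the same set of responders for duration of response in Tables 43 and 44.
- Keep the day-56 tables, including those in section 7.3, as supportive analyses.
- List every patient classified differently by the two definitions, with scan dates and the date of local treatment. If there are none, one sentence closes the matter.

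The cost is SAP wording, one derived variable and one listing. The protocol already calls for the scans, and neither the sample size nor patient management changes.
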